**Table 6. Panobinostat Dose Adjustments for Non-Hematologic Toxicities (continuation)**

AE Term and Description	Panobinostat Dose Modification
GASTROINTESTINAL	
Diarrhea	
Grade 1	Maintain dosing.
Grade 2 or Grade 3  (Despite anti-diarrheal therapy)	1. Interrupt panobinostat until toxicity resolved to ≤ grade 1. 2. Restart treatment with a 1 level dose-reduction (Table 3).
Grade 4	Discontinue panobinostat
Recurrent Event After Initial Dose Reduction	1. Interrupt panobinostat until toxicity resolved to ≤ grade 1. 2. Restart treatment with a second 1 level dose-reduction.
Recurrent Event After 2 Dose Reductions	Discontinue panobinostat
Vomiting	
Grade 1	Maintain dosing.
Grade 2 or Grade 3  (Despite anti-nausea therapy)	1. Interrupt panobinostat until toxicity resolved to ≤ grade 1. 2. Restart treatment with a 1 level dose-reduction (Table 3).
Grade 4	Discontinue panobinostat
Recurrent Event After Initial Dose Reduction	1. Interrupt panobinostat until toxicity resolved to ≤ grade 1. 2. Restart treatment with a second 1 level dose-reduction.
Recurrent Event After 2 Dose Reductions	Discontinue panobinostat
Fatigue	
Grade 4	1. Interrupt panobinostat until toxicity resolved to ≤ grade 2 or baseline. 2. If resolved in 7 days after interruption of panobinostat, then restart panobinostat at an unchanged dose level. 3. If resolved in more than 7 days after interruption of panobinostat, then restart panobinostat with a 1 level dose-reduction.
Other Non-Hematologic Toxicity	
Grade 3	1. Interrupt panobinostat until toxicity resolved to ≤ grade 1 or baseline. 2. Restart treatment with a 1 level dose-reduction (Table 3).
Grade 4	Discontinue panobinostat
Recurrent Event After Initial Dose Reduction	1. Interrupt panobinostat until toxicity resolved to ≤ grade 1. 2. Restart treatment with a second 1 level dose-reduction.
Recurrent Event After 2 Dose Reductions	Discontinue panobinostat

**Table 6. Panobinostat Dose Adjustments for Non-Hematologic Toxicities (continuation)**

Each patient is allowed a maximum of 2 dose reductions (Table 3). No patient will receive less than 15 mg three times weekly. If toxicity recurs at this dose level, panobinostat will be discontinued.
Patients with grade 4 adverse event should be discontinued from further treatment with study drug.
* Common Terminology Criteria for Adverse Events (CTCAE Version 4.0)

 Patients should be instructed to contact their physician at the onset of diarrhea. Each patient should be instructed to have loperamide readily available and to begin treatment for diarrhea at the first episode of poorly formed or loose stools or the earliest onset of bowel movements more frequent than normally expected for the patient. Loperamide 4 mg should be taken at the first loose stool or more frequent than usual bowel movements, followed by 2 mg as needed, no more frequently than every 4 hours not to exceed a total of 16 mg in 24 hours. Patients with diarrhea grade 2 despite this loperamide regimen should interrupt treatment with panobinostat as described in the table. If the above regimen is inadequate then additional evaluation and treatment should be pursued as medically indicated. Premedication with loperamide is not recommended.
 
The use of drugs with laxative properties should be avoided because of the potential for exacerbation of diarrhea. Patients should be advised to contact their physician to discuss any laxative use. Patients should be instructed to contact their physician at the onset of diarrhea.
 
If severe diarrhea (grade 3 and 4) happens, patient should be admitted into the hospital. Replace IV fluids and electrolytes as appropriate. Treatment should follow institutional standard of care or local guidelines.
 
If patient has two grade 3 diarrhea events or vomiting episodes with or without prophylaxis medications, the patient may be discontinued from study drug rather than attempting dose reductions at the discretion of the investigator.

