### 5.2.2. Definitions of Dose-Limiting Toxicity (DLT)

For the purpose of determining the MTD (see Section 5.2.3), DLT is defined as any of the following that are determined to be related to study treatment during **Cycle 1**:

- Grade 4 neutropenia (absolute neutrophil count [ANC] <500/ $\mu$ L) for >7 days.
- Febrile neutropenia (ANC <1000/ $\mu$ L with fever >101°F [38.5°C]).
- Grade 3 thrombocytopenia with  $\geq$  Grade 2 bleeding.
- Grade 4 thrombocytopenia (platelets <25,000/ $\mu$ L) > 7 days (patients may receive platelet support/transfusion).
- $\geq$  Grade 2 neuropathy with uncontrolled pain
- $\geq$  Grade 3 non-hematologic drug-related toxicity (excluding alopecia) despite optimal supportive care lasting >72 hours or requiring a dose reduction in the first cycle.
- Patients who are unable to receive 75% of the required doses of both agents secondary to toxicity.

Adverse events will be graded using the National Cancer Institute (NCI) Common Toxicity Terminology Criteria for Adverse Events v4.0 (CTCAE v4.0).

Dose modifications are not permitted during Cycle 1 in any cohort unless the subject experiences a DLT. Subjects in dose level -1 (see Table 2) who develop a DLT during Cycle 1 will be discontinued from the study. Subjects in dose level 1 or higher who experience a DLT during Cycle 1 will have treatment held. The DLT will be counted toward the assessment of the MTD for the given cohort; however, the subject may continue on therapy if the toxicity resolves and dose modifications can be implemented according to the dose modification guidelines in Section 6.0.

Patients who withdraw from the study before receiving 75% of their scheduled Cycle 1 doses due a non-drug related AE (i.e., tumor progression) will be considered inevaluable and will be replaced.

Patients without clinical evidence of progressive disease at the end of the first cycle of study therapy will continue treatment. Patients will be reevaluated for response after completing 2 cycles (8 weeks) of treatment. Patients with objective response or stable disease according the International Myeloma Working Group Uniform Response Criteria (see Appendix C) will continue treatment, with reevaluations until disease progression occurs, unacceptable toxicity develops, or the subject chooses to discontinue study treatment.

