**Table 5. Panobinostat and Carfilzomib Dose Adjustments for Hematologic Toxicities**

AE Term and Description	Dose Modification	
	Panobinostat	Carfilzomib
THROMBOCYTOPENIA		
Grade 1 or 2	Maintain dosing; monitor as clinically indicated.	Maintain dosing; monitor as clinically indicated.
Grade 3 (25 - <50 x 10  /L)	
 
1. Interrupt study treatment until toxicity reduced to ≤ grade 2a.
 
2. Restart treatment with a 1 level dose-reduction (Table 3).
 
	
 
1. Interrupt study treatment until toxicity reduced to ≤ grade 2a.
 
2. If improves in ≤ 7 days, maintain same dose, if > 7 days reduce dose 1 level.
 

Grade 4 (<25 x 10  /L)	
 
1. Interrupt study treatment until toxicity reduced to ≤ grade 2a.
 
2. Restart treatment with a 1 level dose-reduction.
 
	
 
1. Interrupt study treatment until toxicity reduced to ≤ grade 2a.
 
2. Restart treatment with a 1 level dose-reduction.
 

Recurrent Grade 3/4 Event After Initial Dose Reduction	
 
1. Interrupt study treatment until toxicity reduced to ≤ grade 2a.
 
2. Restart treatment with a second 1 level dose-reduction.
 
	
 
1. Interrupt study treatment until toxicity reduced to ≤ grade 2a.
 
2. Restart treatment with a second 1 level dose-reduction.
 

Recurrent Grade 3/4 Event After 2 Dose Reductions	Discontinue	Discontinue

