Grade 3 ANC $< 1.0 \times 10^9/L$ , fever $\geq 38.5^\circ C$	
 
1. Interrupt study treatment until ANC recovery to <math>\leq</math> grade 2a (<math>ANC \geq 1.0 \times 10^9/L</math>) and resolution of fever <math>< 38.5^\circ C</math>.
 
2. Restart treatment with a 1 level dose-reduction.
 
	
 
1. Interrupt study treatment until ANC recovery to <math>\leq</math> grade 2a (<math>ANC \geq 1.0 \times 10^9/L</math>) and resolution of fever <math>< 38.5^\circ C</math>.
 
2. Restart treatment with a 1 level dose-reduction.
 

Grade 4 ANC $< 1.0 \times 10^9/L$ , fever $\geq 38.5^\circ C$ and life-threatening consequences	Discontinue	
 
1. Interrupt study treatment until ANC recovery to <math>\leq</math> grade 2a (<math>ANC \geq 1.0 \times 10^9/L</math>) and resolution of fever <math>< 38.5^\circ C</math> and any complications.
 
2. Restart treatment with a 1 level dose-reduction.
 

a Repeat labs weekly until recovery.

The criteria for adjusting the dose of panobinostat in the event of non-hematologic toxicities are detailed in Table 6.

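### Table 6 gives two incompatible panobinostat instructions for grade 4 fatigue: its footer stops the drug, its fatigue row restarts it

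*Combined protocol and SAP*

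**What the plan says.** Section 6.1 makes Table 6 the governing text for panobinostat: "The criteria for adjusting the dose of panobinostat in the event of non-hematologic toxicities are detailed in Table 6". The notes at the foot of that table include a general rule: "Patients with grade 4 adverse event should be discontinued from further treatment with study drug".

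The fatigue block has a single entry, for grade 4, with three steps. The first is "Interrupt panobinostat until toxicity resolved to ≤ grade 2 or baseline". The second is "If resolved in 7 days after interruption of panobinostat, then restart panobinostat at an unchanged dose level". The third restarts the drug one dose level lower when recovery takes more than 7 days.

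The Grade 4 entries for diarrhea, vomiting and other non-hematologic toxicity discontinue panobinostat. So do the creatinine and bilirubin entries labelled Grade 3 or 4.

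**The concern.** Permanent discontinuation and planned restart cannot both be carried out for the same patient. One site may apply the footer and stop panobinostat. Another may apply the row and resume at full dose with grade 2 fatigue still present. Both could show that they had followed the protocol. The choice affects the patient's safety and continued access to treatment, and inconsistent handling would make dose-modification and discontinuation data harder to interpret.

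Fatigue is a relevant toxicity for this drug. Section 8.1.5 lists fatigue and weakness among the events seen in at least 30% of patients, all grades together.

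**Working it through.** The plan states no figure on this point, so the check is a comparison of text.

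**Scope.** Fatigue is non-hematologic, so Table 6 applies. The footer speaks of study drug rather than panobinostat, but in a panobinostat table it covers panobinostat on any reading.

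**The two rules by time to recovery**, with the general rules of Section 6 added (a drug held for over 3 weeks is discontinued; a patient on the lowest dose who needs a reduction stops that drug):

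| Grade 4 fatigue, recovery to grade 2 or lower or baseline | Fatigue row with Section 6 | Footer | Same action? |
|---|---|---|---|
| Within 7 days | Restart, same dose | Stop | No |
| After 7 days, hold of 3 weeks or less | Restart one level lower (stop if already at 15 mg) | Stop | No, except at 15 mg |
| Hold of more than 3 weeks | Stop | Stop | Yes |

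The conflict therefore covers grade 4 fatigue that recovers within 3 weeks, apart from the 15 mg case, and is sharpest within 7 days.

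**Rows that name grade 4.** There are seven: creatinine above 3 x ULN, bilirubin above 3 x ULN, the same bilirubin line again under AST/ALT, diarrhea, vomiting, fatigue, and other non-hematologic toxicity. Six discontinue panobinostat (7 - 1 = 6). Fatigue alone restarts it.

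**Reconciling text.** Section 6, Section 6.1, Section 6.3 and the amendment history contain no exception for fatigue and no statement that a row overrides the footer. The 3-week rule limits how long the drug may be held; it does not lift the footer.

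**Link to dose escalation.** Section 5.2.2 counts as a DLT any related event of at least "Grade 3 non-hematologic drug-related toxicity (excluding alopecia) despite optimal supportive care lasting >72 hours". A patient with a Cycle 1 DLT may continue if the toxicity resolves and "dose modifications can be implemented according to the dose modification guidelines in Section 6.0". Related grade 4 fatigue that outlasts 72 hours is thus a DLT whichever Table 6 instruction is followed. The conflict changes what the patient receives afterwards, not the DLT count.

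**The case against.** The best defence is that a specific row prevails over a general note. The fatigue entry is a deliberate three-step rule for one toxicity at one grade, while the footer is one general sentence. Read literally, the footer would also contradict Table 5, where panobinostat after grade 4 thrombocytopenia or neutropenia is to "Restart treatment with a 1 level dose-reduction". The footer must therefore be read more narrowly than its words.

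Part of this stands: the reading is workable and may be what the sponsor intended. But it is unwritten. Confining the footer to Table 6 follows from where it is printed, so Table 5 is not in conflict. Exempting one row inside Table 6 needs a statement that the table lacks, and the other six rows naming grade 4 agree with the footer.

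A reader might also infer that the row's recovery threshold is wrong, because the Grade 3 entry for other non-hematologic toxicity is stricter: "Interrupt panobinostat until toxicity resolved to ≤ grade 1 or baseline". The documents do not support that. Thresholds in Table 6 differ by toxicity (creatinine and bilirubin use 1.5 x ULN; diarrhea is interrupted from grade 2), and nothing shows that grade 2 is unsuitable for fatigue. Nor do they settle whether grade 3 fatigue falls under the other-toxicity rows. Fatigue has its own heading with only a Grade 4 entry, and sending grade 3 fatigue to those rows would be a wider change, possibly affecting more patients than the grade 4 case.

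**Conclusion.** The inconsistency is real and should be corrected. Table 6 prescribes opposite actions for grade 4 fatigue, and the documents give no rule for choosing between them.

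The practical size is small. Section 1.2.1 calls grade 3 and 4 events other than thrombocytopenia uncommon. No grade 4 fatigue rate is given and the CTCAE v4.0 fatigue scale is not reproduced, so any expected number of affected patients would be a guess and none is offered.

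A reader might infer that the conflict distorts the MTD. It does not: for fatigue beyond 72 hours the event is a DLT under either instruction, and Section 5 reports no DLTs in the completed Phase I levels. For a shorter Cycle 1 episode the documents do not say how a stop under the footer would be counted, and nothing here rests on that case. The primary response endpoint is also unaffected: its definition, the 18% and 36% rates and the sample size of 27 do not depend on this rule.

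The conclusion assumes only that the footer applies to the rows of its own table.

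**What to change.** Make Table 6 give one instruction for grade 4 fatigue. There are two ways:

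- Change the Grade 4 fatigue entry to *Discontinue panobinostat*, matching the footer and the other rows that name grade 4. The cost is that a rare patient loses the restart option the row now gives.
- If restart is intended, keep the row and add *except fatigue, see row above* to the footer. No patient loses an option.

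The handling of grade 3 fatigue and the row's recovery threshold are for the sponsor to decide; resolving the conflict requires no change to either. Each option is one wording change in an amendment, with no effect on design, sample size or analysis.

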**6.2. Panobinostat Dose Modifications for Prolonged QTc Interval**

All cardiac events should be treated according to institutional standards and referred to a specialist if clinically indicated. Treatment decisions at the sites will be based on QTc as determined by the automated machine reading (or as measured and calculated by trained personnel at the site). If a patient cannot be dosed due to prolonged QTcF for more than 7 days since last dose, patient should be discontinued from study.

**Table 7: Criteria for Dose Reductions, Delays and/or Re-Institution Due to Drug-Related QTcF Abnormalities**

ECG TIME POINT	ABNORMALITY	DOSE MODIFICATION GUIDELINE
Dose modifications are based on local readings of the average QTcF of triplicate ECGs.		
Cycle 1 Dose Modification Criteria:		
Cycle 1 PRE-DOSE Days 1 and 5 Triplicate ECGs	Day 1: Average QTcF: >450 msec	Check and correct the patient's serum potassium, magnesium, calcium, phosphorus immediately, as well as evaluate concomitant medications. If abnormality noted on Cycle 1 Day 1: Repeat 3 pre-dose ECGs. If the 3 pre-ECGs: Do not meet criteria again, discontinue patient from study. Do meet criteria for dosing; administer panobinostat.
	Day 5: Average QTcF: ≥480 msec to <500 msec Or >60 msec increase from baseline average	If abnormality noted on Cycle 1 Day 5: Delay dose at least 3 days and repeat 3 pre-dose ECGs. If the repeat 3 pre-dose ECGs: Do not meet pre-dose ECG criteria again, discontinue panobinostat. Do meet pre-dose ECG criteria for dosing and QTc prolongation determined to be related to panobinostat, resume panobinostat treatment with a 1-level dose reduction. If however, it was determined that the QTc prolongation was secondary to electrolyte abnormalities or concomitant medications, continue at the same dose level. Repeat ECGs – pre-dose (x3), 3-hours post-dose (x3), on the next scheduled dosing day.
	Average QTcF: ≥500 msec	Check and correct the patient's serum potassium, magnesium, calcium and phosphorus immediately. Discontinue patient from panobinostat.  If however, it was determined that the QTc prolongation was secondary to electrolyte abnormalities or concomitant medications: Omit dose. On the next scheduled dosing day continue at the same dose level. Repeat ECGs - pre-dose (x3), 3-hours post-dose (x3), on the next scheduled dosing day.

**Table 7. Criteria for Dose Reductions, Delays, Re-Institution Due to Drug Related QTcF Abnormalities (continuation)**

ECG TIME POINT	ABNORMALITY	DOSE MODIFICATION GUIDELINE
Dose modifications are based on local readings of the average QTcF of triplicate ECGs.		
Cycle 1 Dose Modification Criteria:		
Cycle 1 POST-DOSE Days 1 and 5 Triplicate ECGs	Average QTcF: ≥480 msec to <500 msec Or >60 msec increase from baseline average	Check and correct the patient's serum potassium, magnesium, calcium, phosphorus immediately, as well as evaluate concomitant medications. Monitor ECG hourly or by telemetry until at least 2 consecutive hourly ECGs performed at least 6 hours post dose are <480. Next scheduled dosing day: repeat 3 pre-dose ECGs. If these 3 pre-dose ECGs: Do not meet pre-dose ECG criteria for dosing (average QTcF ≥480 msec), discontinue patient from study. Do meet pre-dose ECG criteria for dosing (average QTcF <480 msec) and QTc prolongation determined to be related to panobinostat, resume panobinostat treatment with a 1-level dose reduction. If however, it was determined that the QTc prolongation was secondary to electrolyte abnormalities or concomitant medications, continue at the same dose level. Repeat ECGs - pre-dose (x3), 3-hours post-dose (x3) on the next scheduled dosing day.
	Average QTcF: ≥ 500 msec	Check and correct the patient's serum potassium, magnesium, calcium and phosphorus immediately. Discontinue patient from panobinostat. If however, it was determined that the QTc prolongation was secondary to electrolyte abnormalities or concomitant medications: omit dose. On the next scheduled dosing day continue at the same dose level. Repeat ECGs - pre-dose (x3), 3-hours post-dose (x3), on the next scheduled dosing day.

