### **5.1.1. Panobinostat**

#### **PO TIW during weeks 1 and 3 of each 28-day cycle (i.e. D1, 3, 5, 15, 17, 19)**

Dose levels are defined in Table 2.

Panobinostat will be self-administered (by the patient). Patients should be instructed to take their once-a-day oral dose of panobinostat at the same time of each scheduled treatment day. Panobinostat should be taken with a glass of water; the entire dose should be taken over as short a time as possible. Patients should swallow the capsules as a whole and should not chew them. Patients must avoid grapefruit or grapefruit juice and Seville (sour) oranges during the entire study.

If the patient forgets to take his/her dose, the patient may be instructed to take the dose up to 12 hours after the usual time. If more than 12 hours have passed, then the dose should be withheld that day. The patient should be instructed to wait until the next scheduled dose. If vomiting occurs, no attempt should be made to replace the vomited dose. No missed doses should be made-up.

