### ECG QTcF Monitoring

Because of the observed QTc prolongation in several patients receiving panobinostat, to be eligible for this trial, the patient must have a mean QTc interval  $\leq 450$  at baseline. During Cycle 1 of panobinostat, ECG's will be monitored intensively (see Table 1). Prior to C1D1 and C1D5 dosing of panobinostat, all patients will have 3 12-lead ECGs, separated by 5-10 minutes. Triplicate ECGs, separated by 5-10 minutes, will be repeated approximately 3 hours after panobinostat dosing on C1D1 and C1C5. See Section 6.2.1. for additional ECG monitoring guidelines. Refer to Table 6 for management of prolonged QTc interval.

Beginning Cycle 2, patients will have a single ECG prior to the Day 1 panobinostat dose (assuming no QTc prolongation occurred during Cycle 1).

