**6.2.1. General Monitoring Principles**

### 6.2.1. General Monitoring Principles

The following cardiac monitoring guidelines are required for this study:

1. Patients in screening will have a baseline ECG performed to determine eligibility.
2. Enrolled patients will have ECGs collected as defined in Table 1.
3. On treatment days when ECGs are to be obtained, the patient will take their medication in the clinic. Prior to the first dose of panobinostat (Cycle 1, Day 1), the QTcF interval from each of the 3 ECGs must be  $\leq 450$  msec and the average of the pretreatment QTc intervals must be  $\leq 450$  msec before the patient is dosed. This real-time assessment will be based on the QTc intervals as determined at the clinical center.
4. If the patient does not meet the QTc criteria for dosing, the patient's serum potassium, magnesium, calcium and phosphorus must be measured immediately, and the patient must receive supplements to correct any low values.
5. If the patient experiences a QTcF  $> 480$  msec in Cycle 1 or in any subsequent cycle, the Cycle 1 ECG monitoring schedule will be repeated until they have a treatment cycle with no QT prolongation.
6. At any time, if any ECGs (baseline or post-dose) demonstrate a QTc value  $\geq 480$  msec the Investigator must notify the Sponsor immediately. In addition, the patient's serum potassium, magnesium, calcium and phosphorus must be measured immediately, and the patient must receive supplements to correct any low values.
7. All ECGs will be reviewed by the treating physician prior to administering the dose of panobinostat.
8. In general, panobinostat dose reductions or discontinuations will occur in the following circumstances:
  - Repeat dosing delays due to prolonged QTc intervals
  - QTc  $\geq 480$  msec but  $< 500$  msec (in absence of electrolyte abnormalities).
  - Any QTc  $\geq 500$  msec (discontinuation).

For patients requiring a dose reduction, 3 pre-dose ECG's will be done on the first day of the new lower dose, and 3-hours post-dose (x 3).

If however, it was determined that the QTc prolongation was secondary to electrolyte abnormalities or concomitant medications, panobinostat may be continue at the same dose level. ECGs will be repeated - pre-dose (x3), 3-hours post-dose (x3), on the next scheduled dosing day.

9. Any QTc  $\geq 500$  msec will lead to discontinuation of the panobinostat.

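### Table 7 can re-dose a patient on Day 3 with the same unresolved QTcF rise of more than 60 msec that delays the dose on Day 5

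*Combined protocol and SAP*

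**What the plan says.** **Post-dose row (Table 7, Cycle 1 Days 1 and 5).** It is entered on an average QTcF of 480 to below 500 msec, or on a rise of more than 60 msec from the baseline average. It calls for electrolyte correction, medication review, hourly ECG or telemetry, and triplicate ECGs before the next scheduled dose. An average of 480 msec or more at that point takes the patient off study. Otherwise dosing resumes. The condition for resuming one level lower reads "pre-dose ECG criteria for dosing (average QTcF <480 msec) and QTc prolongation determined to be related to panobinostat". If the prolongation is put down to electrolytes or other drugs, the dose is unchanged.

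**Pre-dose row (Table 7, Cycle 1 Day 5).** It uses the same two limbs, 480 to below 500 msec or more than a "60 msec increase from baseline average". Its instruction is "Delay dose at least 3 days and repeat 3 pre-dose ECGs". A second failure stops panobinostat.

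**Surrounding text.**
- Section 5.1.1.1 schedules the Day 5 readings: "Prior to C1D1 and C1D5 dosing of panobinostat, all patients will have 3 12-lead ECGs, separated by 5-10 minutes".
- Section 6.2.1, item 7: "All ECGs will be reviewed by the treating physician prior to administering the dose of panobinostat".
- Section 6.2 removes from study a patient who cannot be dosed because of prolonged QTcF for more than 7 days after the last dose.
- Panobinostat is given on Days 1, 3, 5, 15, 17 and 19 (Section 5), so the next dosing day is Day 3 after a Day 1 trigger and Day 15 after a Day 5 trigger.

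**The concern.** The post-dose row has two ways in and only one test for re-dosing. A patient who enters on the rise alone is, by definition, below 480 msec, so the reading that raised the alarm already satisfies the test meant to clear it. For that patient the test does not check recovery. The Day 5 row, two days later in the same patient, treats the same reading as a reason not to dose. Nothing in Sections 5.1.1.1, 6.2 or 6.2.1 reconciles the two; item 8 of 6.2.1 lists repeat delays, 480 to below 500 msec, and 500 msec or more, but no rise from baseline.

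At stake is a further panobinostat dose on top of an unresolved rise, with a drug whose QTc risk the protocol itself describes.

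**Working it through.** The plan states no figure on this point, so the check is of the rules themselves, followed by the likely size.

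**1. Where the rules conflict.** The rise trigger needs QTcF > baseline + 60. The re-dosing test needs QTcF < 480. Both hold when baseline + 60 < QTcF < 480, which requires a baseline average below 420 msec. Eligibility allows up to 450, so baselines of 420 to 450 are unaffected. In whole msec:

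| Baseline average | QTcF dosed on Day 3 but delayed on Day 5 |
|---|---|
| 380 | 441–479 |
| 400 | 461–479 |
| 410 | 471–479 |
| 418 | 479 only |
| 419 or more | none |

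**2. Example.** Baseline 400; Day 1 post-dose 465. The rise is 465 − 400 = 65 > 60, so the row is triggered.
- Day 3 pre-dose, unchanged at 465: 465 < 480, so the patient is dosed.
- Day 5 pre-dose, unchanged at 465: 65 > 60, so the dose is delayed at least 3 days.

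**3. Effect of a two-limb test.** The rules were run over whole-msec baselines 360 to 450 (360 is an assumed lower end) and QTcF up to 499. Requiring on Day 3 both < 480 and a rise of no more than 60 leaves 0 conflicting combinations.

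**4. How many patients (Section 1.2.2).**
- *Three times weekly.* 12 patients rose by more than 60 msec. Reading the 5 patients as 480–500 and the 3 as above 500, at most 8 exceeded 480, so at least 12 − 8 = 4 did not. The stated denominator is 532, but the printed percentages imply about 587 (98/0.167 = 587). 4/532 = 0.75% and 4/587 = 0.68%; times 80, that is 0.60 and 0.55 patients.
- *Every other week, the schedule used here.* 4 of 70 rose by more than 60 and at most 1 exceeded 480, so at least 3/70 = 4.3% (exact 95% CI 0.9–12.0%). Times 80, that is 3.4 (0.7–9.6).
- *Panobinostat with bortezomib (Section 1.2.3).* No rise above 60 msec in 2,200 ECGs; if all 38 patients contributed, 0/38 has an upper limit of 9.3%.

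**5. Doses and days if Day 3 is withheld after a Day 1 trigger.** Cycle 1 has 6 panobinostat doses.
- Day 3 withheld: 5/6 = 83%.
- Day 3 withheld and Day 5 also lost: 4/6 = 67%. The current text would leave the same patient at 5/6.
- Retest on Day 5: 5 − 1 = 4 days since last dose.
- If the rise persists, earliest repeat is Day 5 + 3 = Day 8, and 8 − 1 = 7 days, which is not more than 7. A Day 9 repeat is 8 days and meets the discontinuation rule; under the current text (last dose Day 3) it is 6.

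**6. After a Day 5 post-dose trigger.** The next dosing day is Day 15, and 15 − 5 = 10 days, already more than 7 because of the planned rest week.

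**The case against.** The best defence is that this is a graded scheme: the rise is an early warning, and 480 msec is the stopping limit. Release from hourly monitoring, repeat monitoring, sponsor notification and item 8 of Section 6.2.1 all use absolute limits. The post-dose row does not ignore the rise either; it brings monitoring, correction, repeat triplicates and, if drug-related, a lower dose.

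That accounts for the 480 limit but not for the conflict. Days 3 and 5 are both pre-dose readings two days after the previous scheduled dose, and no reason is given to treat them differently. Nor does the dose reduction explain it: the Day 5 row has the same reduction, but only after a delay and a passed repeat.

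Four stronger readings might be inferred, and the documents do not support them.
- *That sites have no rule.* Each day has an explicit instruction; the fault is that the two disagree.
- *That the Day 5 row leaves its criteria undefined.* It speaks of failing the criteria *again*, which points to the abnormality printed beside it.
- *That Section 1.2.2 gives the rate of affected patients.* Its counts include doses above 20–30 mg, are not confined to Cycle 1 post-dose readings, and say nothing of persistence to the next dosing day.
- *That Table 7 already contains a withhold-and-retest step for a drug-related rise.* The step in the rows for 500 msec or more, "omit dose. On the next scheduled dosing day continue at the same dose level", applies only when electrolytes or other drugs are the cause.

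**Conclusion.** The concern holds as a minor inconsistency in a cardiac-safety rule. It follows from the wording of Table 7 and does not depend on a rate. It affects only patients with a baseline average below 420 msec, a rise-only trigger, and a rise that persists to the next dosing day. The plausible number is none to a few in 80.

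After a Day 1 trigger, exposure is about one dose, given after physician review and repeat triplicates, and the Day 5 triplicates would catch a persisting rise. A reader might infer that patients are re-dosed at full dose without protection; they are not, since a drug-related rise means a one-level reduction and the other safeguards still apply. The counts rest on reading the Section 1.2.2 categories as 480–500 and above 500 msec.

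**What to change.** **Day 1 post-dose trigger.** State in Table 7 that the Day 3 pre-dose criteria are an average QTcF below 480 msec and no more than 60 msec above the baseline average. If QTcF is below 480 but the rise is still more than 60, withhold Day 3 and retest with the Day 5 triplicates. If the criteria are then met, resume under the row's existing dose rule. If the rise persists, apply the existing Day 5 row with the repeat on Day 8. Keep discontinuation for 480 msec or more.

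**Day 5 post-dose trigger.** Use the two-limb test on Day 15 only if the amendment also says that the 7-day rule in Section 6.2 does not count the planned rest week. Otherwise leave this path unchanged; withholding Day 15 under the rule as written could take a patient below 480 msec off study.

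**Cost.** About two sentences in an amendment, plus one on the 7-day rule if the Day 5 path is included. No new ECG visit is needed for the Day 5 retest. The downsides are:
- One withheld dose leaves 83% of Cycle 1 panobinostat. It cannot be recovered, since Section 5.1.1 says "No missed doses should be made-up".
- If Day 5 is also lost, 67% may count toward the dose-limiting toxicity criterion in Section 5.2.2, "Patients who are unable to receive 75% of the required doses of both agents secondary to toxicity", should a shortfall in one agent be enough.
- There is no slack beyond Day 8 before the 7-day rule applies.
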